Study Population Participants will consist of 60 Veterans with chronic pain and active suicide ideation. Participants will be randomized to either remote Problem-solving Treatment or remote attentional control (n=30/group). Consistent with recommendations for preliminary analyses, sample size was determined based on estimates of feasibility during the study timeframe.^{90,91}

Subject Identification and Recruitment: Any Veteran who resides within the United States may be invited to participate in the study. During the phone screening, we will request verbal consent and inclusion/exclusion criteria will be evaluated. Veterans may be recruited from anywhere in the nation. Potential participants may be identified through the following: VINCI, VISTA and/or CPRS, REACH VET, the Managerial Accounting Office (MCAO), the VA Epidemiology Program, the VA Office of Public Health Gulf War Registry, the Defense Manpower Data Center (DMDC) of the Department of Defense (DoD), VADIR (Veteran Administrative DoD Identity Repository), WRIISC Clinical and Operations Databases. We may also reach out to Veterans who have both participated in recent studies and expressed interest in being contacted. We will request from VINCI, the DMDC, VADIR, the VA Epidemiology Program, and VA Office of Public Health Gulf War Registry to provide a list of Veterans who possibly meet our inclusion criteria and reside nationally. Data elements requested can include the following: name, date of birth, social security numbers, address, contact phone number(s), vital statistics, period of combat (combat pay records) and/or service medals, status of deployment.

We will also use the following methods to identify and recruit potential participants: referrals, standard mail, telephone, flyers, and advertisements. This includes: 1. planned conferences, satellite broadcasts, and other educational workshops or meetings for providers or Veterans; 2. VA facilities and affiliated ambulatory services including community-based outpatient clinics (CBOCs); 3. community locations (e.g., Home Depot); 4. Veteran-related events such as job fairs; 5. newspapers/newsletters; 6. websites relevant to Veterans (e.g., American Legions); 7. VA and Veteran-related social media; and 8. websites relevant to recruitment (e.g. clinicaltrials.gov).

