This attentional control has been recently used successfully as a control group in large clinical trials for suicide prevention.⁹² Attentional control is thought to encompass common therapeutic factors, (e.g., therapeutic alliance, emotional support), while excluding the factors specific to the active treatment condition (e.g., skill building, use of behavior change techniques and outside practice).

Data Monitoring Plan: A three-person Data and Safety Monitoring Board (DSMB) will be recruited to oversee and monitor the safety of study participants and the validity and integrity of the research endeavor. The first meeting of the Board will establish the DSMB procedures. We plan for the board to be independent of the study and include: expert in suicide prevention, biostatistician and facility leader at the VA NJHCS (e.g., head of mental health).

It was decided that the DSMB will meet twice a year and more often as needed both with and without the investigators present. The full DSMB will determine when and if the investigators will attend. The chair of the DSMB will rotate among the three members, with each member serving as chair for one year.

Proposed DSMB Procedures: The VANJHCS IRB will be informed of the DSMB procedures - and the names of the board members - established during this initial meeting. The IRB will evaluate the monitoring procedures and recommend modifications if necessary.

Once a year, the PI will send information to the DSMB on recruitment progress (screened, declined, enrolled, excluded, medical stability considerations for inclusion/exclusion in study, active in study, lost to follow-up), treatment completion rates, serious adverse events, and rates of re-hospitalization and suicide attempts. Study personnel will maintain a running tally of this information throughout the life of the study and will report the information separately by study condition. IRB continuing review documents will also be provided to the DSMB. DSMB members will receive this material for review in advance of scheduled meetings.

The following events would be reportable to the DSMB as soon as they are recognized:

- a) Serious Adverse Events (SAE) (as defined in VHA Handbooks 1058.01 & 1200.05) that are related to study procedures or occur at a rate that is at least 25% higher in one condition compared to the other.
- b) New information which alters the risk: benefit ratio of participating in the study
- c) Events compromising data confidentiality.

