When a participant is withdrawn from the research for safety concerns, our team will retain clinical responsibility until continuing care is successfully transferred to the appropriate provider (e.g., emergency department, hospitalization, psychiatrist, local suicide prevention coordinator, primary care provider). The following situations will necessitate participant withdrawal from the research (but not clinical care):

- Suicide attempt
- Indication that participant has developed definite intent to carry out a suicide plan, as measured by endorsement of item 5 on Section I of the C-SSRS.
- In addition, if there is a significant increase in the severity of suicidal ideation the participant will be reviewed by an internal study safety team comprised of 3 study investigators to determine appropriateness for continued participation. Increased risk will include an increase of 2 points on the C-SSRS from a participant's baseline level (e.g., moving from a baseline C-SSRS score of 2 [i.e., thoughts of killing oneself without any associated method or intent] to a C-SSRS score of 4 [i.e., suicidal thoughts with some, limited intent to act on them]).

Data Analysis Plan: We will explore the data using scatterplot graphs and calculating the means, standard deviations, proportions, histograms, etc. to explore the distributions of the data, identify outliers and calculate correlations between variables. We will calculate the percent change from baseline for each measure. We will also calculate the effect size (Cohen's D) for the change in each arm from pre to post treatment and calculate the effect size of the change in treatment between arms. Consistent with best practices for preliminary data analysis, we will not calculate statistical significance as we are not be powered to find an effect.^{90,91} The analyses will be conducted with intent to treat approach.

Best practices for determining improvement in executive functioning include using self-report, objective and support person report. While it is not expected all measures will show improvement due to variability in the assessment approaches, there should be an indication of clinically significant improvement across multiple assessments. Our preliminary data is consistent with previous research that finds PST has a moderate effect on self-report of problem-solving deficits (Cohen's D >0.22)^{45,46} as

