Assessment of treatment integrity	Direct observation in peer supervision; therapy checklist after each session; record length of time for each session.	Direct observation in individual and peer supervision.	Direct observation in individual and peer supervision.
Accuracy of data	A random sample (20%) of collected tapes is examined, sampled across study providers, treatment phases, situations, cases and sessions.		Code the control for use of PST.
Rating integrity	Raters are highly trained; interrater reliability is assessed; multiple raters are used.		
Operational definition	Specific treatment manual with information about the theory & sequencing of techniques.		
Training of providers	Three days of didactic instruction for each treatment; listen to treatments delivered by other providers; role-play with other providers; on-going bi-weekly feedback and peer training.		
Supervision of study providers	Study providers attend twice-weekly peer & weekly individual supervision; supervision includes observation; review of adherence checklists; if a study provider fails to meet criteria s/he will receive more intensive supervision.		

Assessments: Assessments will consist of the Veterans completing questionnaires and a short battery of neuropsychological tests. Additionally, the specified support person of the Veteran will be asked to complete questionnaires. Veterans (and their support person) can complete the questionnaire packets

through Qualtrics, the U.S. mail (the packet would be mailed to the Veteran along with a pre-paid envelope to return the packet), and/or over the telephone with a member of the study team. The neuropsychological battery will be completed through Millisecond's Inquisit Web, a software package designed to administer neuropsychological measures online, as well as over the phone to administer the means-end problem-solving task. We will make a concerted effort to remind Veterans with letters and phone calls to complete and return questionnaires, and also to complete the neuropsychological battery. If needed, we will resend questionnaire packets to Veterans and/or their support person. We will also collect data from the Veterans' medical record about their diagnoses, treatments, medications.

Assessments will be completed at four time points:

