Caregiver Social Problem-Solving Inventory-Revised (SPSI)⁷⁰. A support person of the Veteran will be identified by the patient and invited to complete the SPSI to provide their perspective of the patient's problem-solving ability.

Secondary Outcome:

Interpersonal Needs Questionnaire (INQ).⁸⁰ Feelings of burdensomeness and belongingness will be measured by the Interpersonal Needs Questionnaire (INQ). The INQ is an 18-item self-report questionnaire. Scale items have high levels of internal consistency, and findings from prior investigations have also supported the construct, convergent, and predictive validity of this measure.

Exploratory Outcome:

Columbia-Suicide Severity Rating Scale (C-SSRS).²⁶ The C-SSRS is the gold standard for suicide assessment and measures level and intensity of suicidal ideation, planning and preparation for suicidal behavior, and method and lethality of recent and past lifetime suicidal behavior. During assessment, this measure will be administered by study personnel. To determine eligibility, we will use the level of suicidal ideation. Patients will be eligible who have a score of 2 (have you actually had any thoughts of killing yourself?), 3 (have you been thinking about how you might do this?) or 4 (Have you had these thoughts and had some intention of acting on them?). The intensity of ideation subscale (the summed score from five

separate items on Part II of the C-SSRS; subscale range = 2-25) will be the primary dependent variable for the fully powered clinical trial. The intensity of ideation asks about the intensity of ideation in the past 6 months (e.g., the frequency, duration controllability).

Suicide Ideation Questionnaire (SIQ).⁸¹ The SIQ is a 30-item self-report instrument designed to assess thoughts about suicide experienced during the prior month. SIQ has strong internal consistency ($\alpha = .97$) and construct validity. This measure will allow for supplementary investigation of ideation.

Suicide-Related Coping Scale.²⁷ The Suicide-Related Coping Scale captures an individual's perceived ability to use internal and external coping to problem-solve suicidal thoughts and urges. This measure was validated in a Veteran sample. The items in this measure capture the types of skills we expect Veterans to be able to use after learning problem-solving (i.e., "I recognize the circumstances that make me suicidal")

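### Suicide-attempt rates go to the DSMB by arm, but no stated source, window or denominator covers Veterans who are withdrawn, lost or never reassessed

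*Combined protocol and SAP*

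**What the plan says.** - **Reporting.** Under Proposed DSMB Procedures, the yearly information to the board includes "serious adverse events, and rates of re-hospitalization and suicide attempts". Study staff keep a running tally and "will report the information separately by study condition". The same section makes serious adverse events reportable at once if they are related to study procedures or "occur at a rate that is at least 25% higher in one condition compared to the other".
- **Instrument.** The C-SSRS is the only instrument described as covering suicidal behaviour, including "method and lethality of recent and past lifetime suicidal behavior" (Exploratory Outcome). In Table 2 it is given at screening, baseline, post-treatment and 6 months. The Suicide Ideation Questionnaire covers thoughts only.
- **Contact.** Providers in both arms check risk weekly as part of treatment (Procedure). Under Assessments, the post-treatment and 6-month assessments are both timed from the 12th session.
- **Withdrawal.** The Safety Plan introduces its list with "The following situations will necessitate participant withdrawal from the research (but not clinical care". A suicide attempt and endorsement of C-SSRS item 5 are both on it. No later collection of attempts is described for these Veterans.
- **Records.** Under Assessments, the team will take data from the "medical record about their diagnoses, treatments, medications". Attempts and deaths are not listed. No time window is given, and no rule for withdrawn Veterans.

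**The concern.** A rate by arm needs a source that works the same way for everyone randomised, a window and a denominator. The plan gives none of these for attempts. Weekly contact ends with the sessions, and the next scheduled contact is a single assessment about six months later. Three groups can fall outside it: Veterans withdrawn for item 5, Veterans lost to follow-up, and Veterans who stop early and so have no defined assessment date, because both later assessments are counted from session 12.

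If these groups differ in size between arms, the arm that loses more people can look safer for that reason alone. Detection may also differ during treatment. The Problem-solving Treatment section describes weekly assessments and suicidal-ideation monitoring, whereas the Attentional control section relies on the provider's clinical judgment. With 30 Veterans per arm, one unseen attempt can change what the board reads.

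**Working it through.** The documents give no event rate, loss rate or power figure for attempts. Of the trial's size they say that "sample size was determined based on estimates of feasibility during the study timeframe". There is therefore no stated figure to reproduce beyond the length of follow-up.

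**1. Follow-up resting on one assessment.** Twelve weekly sessions last 12 × 7 / 30.4375 = 2.76 months. Adding 6 months gives 8.76, which agrees with the roughly 9 months under Research Design and Methods. The part after sessions end is 6 / 8.76 = 0.685.

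**2. Expected events.** With an assumed attempt risk of 3%, 5% or 10%, each arm of 30 expects 30 × 0.03 = 0.9, 30 × 0.05 = 1.5 or 30 × 0.10 = 3.0 attempts.

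**3. Share of attempts missed.** Let L be the share of Veterans lost and R their attempt risk relative to those retained. Both are assumptions.

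- No ascertainment at all: share missed = L·R / (L·R + 1 − L).
- Only the 6-month visit missed, with constant hazard and everything up to post-treatment captured: the same expression × 0.685.

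| L | R | No ascertainment at all | Only 6-month visit missed |
|---|---|---|---|
| 20% | 1 | 0.2/1.0 = 20% | 14% |
| 20% | 2 | 0.4/1.2 = 33% | 23% |
| 20% | 3 | 0.6/1.4 = 43% | 29% |
| 30% | 1 | 0.3/1.0 = 30% | 21% |
| 30% | 2 | 0.6/1.3 = 46% | 32% |
| 30% | 3 | 0.9/1.6 = 56% | 39% |

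A Veteran withdrawn partway through treatment lies between the two columns.

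**4. Unequal loss with equal true risk.** Take R = 1, all randomised as denominator, and assumed losses of 10% and 28%.

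- No ascertainment at all: apparent rate ratio = (1 − 0.10)/(1 − 0.28) = 1.25. This equals the 25% margin in the serious-adverse-event reporting rule.
- Only the 6-month visit missed: (1 − 0.10 × 0.685)/(1 − 0.28 × 0.685) = 0.9315/0.8082 = 1.15.
- Attempts found for everyone randomised: 1.00.

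**5. Chance.** Treat the observed counts as independent binomials with n = 30 and probability p(1 − d), where d is the share unascertained. At p = 5% and no loss, the probability that a given arm is at least 25% higher is 0.38. With 10% versus 30% wholly unascertained it becomes 0.44 for the better-followed arm and 0.29 for the other. Loss shifts a comparison that is already noisy.

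**The case against.** The strongest reply is that attempts have several routes into the tally besides the C-SSRS, and much of it stands.

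- Weekly check-ins run in both arms. Staff try to call after missed sessions (Minimizing Attrition). Usual-care providers are invited to contact the team (Communication with Other Providers). A suicide attempt is itself a trigger for contacting the medical monitor, with no instrument attached. Recorded diagnoses or treatments could reveal a treated attempt.
- The C-SSRS looks back, so a Veteran who stops sessions but completes a later assessment can still report earlier attempts. Nothing in the plan says that stopping sessions ends assessment.
- The board also sees loss to follow-up and treatment completion by condition, and its planned membership includes a biostatistician.

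A reader might infer that the C-SSRS is the only way an attempt can be known, and that attempts in everyone who stops or withdraws are lost. The documents do not support that. An attempt that triggers withdrawal is known by definition. If the rate counts Veterans with any attempt, repeat attempts by the same person do not change it.

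The reply does not close the gap. The check-ins and missed-session calls belong to the session schedule. The reporting rules say what to do once an event is recognised, not how to find one in a Veteran out of contact. Lookback helps only those reassessed. Seeing unequal loss warns the board but does not recover the events. A first attempt after an item 5 withdrawal has no stated route.

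**Conclusion.** The point holds as a gap in ascertainment: attempts among withdrawn, lost or never-reassessed Veterans can be missed, and unequal loss can distort the by-arm safety tally. It is worth correcting.

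For a missed 6-month visit alone, the size is about 14% to 29% of attempts at 20% loss and 21% to 39% at 30% loss, over risk ratios of 1 to 3. This assumes a constant hazard and full capture up to post-treatment. Attempt risk, loss and risk ratios are all assumptions.

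Three stronger readings should be set aside.

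- The ranges of 20% to 43% and 30% to 56% apply only to Veterans with no ascertainment at all, not to those who miss one visit.
- A reader might suppose that the Veterans at highest risk are the ones lost. The documents give no evidence either way, which is why a risk ratio of 1 is included.
- This is not bias in an efficacy comparison. Attempts are not an outcome under Aim 1 or Aim 2, and the Data Analysis Plan has no significance tests. Full ascertainment would not make so small a tally precise; it would remove an avoidable distortion.

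**What to change.** Under Assessments, extend the planned VA record review to suicide attempts, suicide-related admissions and deaths. Apply it to every randomised Veteran in both arms, whatever their session, assessment or withdrawal status, unless the Veteran has revoked authorisation. Use one fixed window from randomisation, long enough to cover the scheduled 6-month assessment. A cut-off at 9 months would leave almost no room, since weekly sessions plus 6 months already take 8.76 and sessions may be delayed or added.

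Confirm that the consent and HIPAA text allows record review after withdrawal, and add a sentence if it does not. Those pages are not in the public copy, so this cannot be checked here.

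Report Veterans with at least one event by arm, with all randomised as denominator, beside C-SSRS counts for the same window and the number who revoked.

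The cost is a few abstraction fields and no extra visits. Every participant has a VA primary care provider and a recent VA visit under the Inclusion Criteria, and the team already uses VA records. The limitation is that events treated only outside VA, or never treated, will still be missed. The change alters no clinical or withdrawal rule.

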Patients with chronic pain in the US (100 million)⁷ have 2.6-times greater risk of suicide⁸⁻¹¹ and those on long-term opioid treatment are at even greater risk. Unfortunately, they often do not receive mental health treatment and thus do not receive suicide prevention interventions.¹² They do receive frequent healthcare for their pain^{13,14} providing an unmet opportunity to integrate suicide prevention into their treatment for pain. Problem-solving Treatment (PST) is an evidence-based approach that is available where patients want to receive treatment (e.g., primary care) and is efficacious for chronic pain.^{15,16} Importantly, PST targets problem-solving deficits which are known to increase risk of suicide, suggesting PST could be leveraged to reduce suicide risk. Deficits in problem-solving (an executive function used to find solutions to difficult issues)¹⁷⁻¹⁹ directly increase suicidal risk because they keep patients with active suicidal ideation from generating solutions to their problems (e.g., chronic pain), other than through suicide.^{3,20-22} Deficits in problem-solving also make it difficult to keep pain from impairing daily activities and social relationships. This indirectly increases suicide risk because impairment in daily activities increases feelings of burdensomeness and impairment in social relationships increases feelings of not belonging.²³ Feelings of burdensomeness and of not belonging are key theoretical pathways to suicidal behavior.²⁴

Research Design and Methods: This treatment study will be a randomized controlled trial with two arms: remote Problem-solving Treatment versus remote attentional control. Up to 1,000 Veterans will be screened and up to 60 Veterans will be enrolled. Subject participation will occur over the course of

approximately 9 months; Figure 1 outlines the study methods. Additionally, we will be asking enrolled Veterans to identify their support person (e.g., significant other, caregiver, spouse, partner, family member, friend) and we will invite the identified support person to complete a questionnaire and provide their perspective on the Veteran's problem-solving ability.

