Following each meeting of the DSMB, the DSMB Chair will prepare and send a brief summary report to the PI. The report will document that: (1) a review of recruitment, data and outcomes has occurred, (2) the number, nature, and outcome of any AEs occurring during the review period, and (3) reflect the date the review took place. The report will also inform the PI of the board's conclusion with respect to study progress, any need for modification of the study protocol or operating procedures, and

approval/disapproval for the study to continue. Upon receipt of the report, the PI will be responsible for transmitting a copy of the report to the IRB.

Medical Monitor

In addition to the DSMB, the study will engage a medical monitor. The principal investigator and/or head study provider will reach out to the study monitor within 24 hours through phone and if needed encrypted email for consultation in the following situations:

- Suicide attempt
- Indication that participant has developed definite intent to carry out a suicide plan, as measured by endorsement of item 5 on Section I of the C-SSRS.
- If there is a significant increase in the severity of suicidal ideation the participant. Increased risk will include an increase of 2 points on the C-SSRS from a participant's baseline level (e.g., moving from a baseline C-SSRS score of 2 [i.e., thoughts of killing oneself without any associated method or intent] to a C-SSRS score of 4 [i.e., suicidal thoughts with some, limited intent to act on them]).
- If a participant baseline score on the C-SSRS is a 4.

We will work with the medical monitor to update these procedures as needed.

Clinical Monitoring

NIH Clinical site monitoring is conducted to ensure that the rights and well-being of human subjects are protected, that the reported trial data are accurate, complete, and verifiable, and that the conduct of the trial is in compliance with the currently approved protocol/amendment(s), with GCP, and with applicable regulatory requirement(s). The main features are below.

- Monitoring for this study will be performed by NIMH Clinical Trials Operations Branch (CTOB) monitors.
- Monitoring will be conducted on-site or virtually, throughout the study, and involve targeted data verification of key data variables
- The site PI will be provided copies of monitoring reports within 10 days of visit.

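### A suicide attempt judged unrelated reaches the DSMB promptly only if the SAE tally happens to be unbalanced; naming attempts and deaths on the immediate-report list is a cheap improvement.

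*Combined protocol and SAP*

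**What the plan says.** Proposed DSMB Procedures gives three kinds of event for immediate report to the Board. Item (a) covers SAEs "that are related to study procedures or occur at a rate that is at least 25% higher in one condition compared to the other". Item (b) is new information bearing on risk and benefit. Item (c) is breaches of data confidentiality. Suicide attempts appear in none of them by name.

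Attempts do appear in the routine flow: "Once a year, the PI will send information to the DSMB", and that package includes SAEs and attempt rates, tallied by study condition. The Data Monitoring Plan also states: "It was decided that the DSMB will meet twice a year", with extra meetings when required. After every meeting the chair reports on the adverse events of the review period.

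Two other sections act on any attempt, with no test of relatedness. Under Medical Monitor, the principal investigator or head study provider contacts the monitor "within 24 hours through phone and if needed encrypted email for consultation". Under Safety Plan, an attempt ends research participation.

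**The concern.** The trial enrols Veterans with active suicidal ideation (C-SSRS 2 to 4). The Risks and Side Effects section itself foresees deterioration unrelated to participation. For an attempt put in that category, prompt notice to the Board depends on a comparison of arm counts and not on the attempt itself. Two participants with the same event could be handled differently only because of what had happened in the other arm.

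The Board is the body that receives the by-condition figures. The medical monitor is consulted on individual cases, and nothing in the text has the monitor inform the Board. The question is thus whether the 25% clause can serve as the trigger for unrelated events, and how long an event that misses it would wait.

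**Working it through.** **Inputs from the documents.** Sample size: "up to 60 Veterans will be enrolled", 30 per arm (Study Population). Basis: "sample size was determined based on estimates of feasibility during the study timeframe", so no power or error rate is attached to any safety rule. The clause sets a 25% difference in either direction, with no minimum count, no look schedule and no rule for an arm with zero events. There is no stated operating characteristic to reproduce.

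**Assumptions.** The documents give no expected SAE count, so the total T is varied. A suicide attempt is taken to be an SAE (the definition is by reference to handbooks outside the documents). The 25% is read as relative, and a count against zero as a trip.

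**Where the clause is silent.** It trips when larger/smaller ≥ 1.25. Up to T = 10 the closest unequal split is 5-4, and 5/4 = 1.25, which trips. So up to T = 10 only exact ties leave it untripped. If the tally pools all SAEs, a tie can consist of attempts in one arm and other SAEs in the other.

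**How often an event falls in a silent state.** With equal true rates and a running tally checked after each event, the chance of a tie after an even number k of events is C(k, k/2)/2^k: 50%, 37.5%, 31.25%, 27.3% and 24.6% for k = 2, 4, 6, 8 and 10. The average share of events that leave the clause untripped is:
- T = 2: 0.50/2 = 25%
- T = 4: (0.50 + 0.375)/4 = 22%
- T = 10: (0.50 + 0.375 + 0.3125 + 0.273 + 0.246)/10 = 17%

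The chance that at least one event does so is 50% at T = 2, 62% at T = 4 and 75% at T = 10.

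**What a trip means.** With equal true rates the split is Binomial(T, 0.5). For T ≤ 10, P(trip) = 1 − P(tie); for T = 4 this is 1 − 6/16 = 62.5%. The last two columns vary the convention.

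| Total SAEs | Trips by chance | Zero arm not evaluable | One SAE per person, 30 v 30 |
|---|---|---|---|
| 1 | 100% | 0% | 100% |
| 2 | 50.0% | 0% | 49.2% |
| 3 | 100% | 75.0% | 100% |
| 4 | 62.5% | 50.0% | 61.2% |
| 5 | 100% | 93.8% | 100% |
| 6 | 68.8% | 65.6% | 67.1% |
| 7 | 100% | 98.4% | 100% |
| 8 | 72.7% | 71.9% | 70.6% |
| 9 | 100% | 99.6% | 100% |
| 10 | 75.4% | 75.2% | 73.1% |

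If 25% means percentage points, the arms must differ by 0.25 × 30 = 7.5, that is 8 participants. The chance is then 0% through a total of 7 and at most about 7% through a total of 40.

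On the relative reading a trip barely separates a real difference from none. With two Binomial(30, p) counts, it trips 75% of the time at 5% in both arms and 84% at 5% against 10%. If SAEs are very rare it may not trip at all: at 1% per arm the overall chance is 40%, because 55% of such trials would have no SAE.

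**Delay for events that miss the list.** With one package a year the wait is up to 12 months. If adverse-event data go to each of two meetings, it is about 12/2 = 6 months. Treatment is 12 weekly sessions.

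**The case against.** The strongest reply is that a clause which trips easily sends more notices, not fewer. This stands. On the relative reading the first SAE (1 v 0) is always reportable, and only about 17% to 25% of events at totals of 2 to 10 fall in a silent state. A reader might infer from the chance-trip figures that attempts go unreported because the clause is oversensitive. That does not follow. The reporting gap comes from its silence at ties; the chance trips show a separate weakness, that it carries little information about a true difference.

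A reader might also infer that the Board would learn late of an imbalance in attempts. Mostly it would not, since an imbalance is what trips the clause. The exception is attempts in one arm offset by other SAEs in the other.

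Twelve months is the worst case. The Board can meet more often, and its report after each meeting presupposes current adverse-event data. Item (b) offers a further prompt route, but a discretionary one.

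Nor is there a clear conflict with blinding. Randomization Procedures blinds the investigators, while the study coordinator randomizes and study personnel keep the by-condition tally. What remains is that the principal investigator, stated to be blind, is the one who sends the package.

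Finally, the procedures are headed as proposed, are to be settled at the Board's first meeting and are open to IRB modification. Any attempt brings medical-monitor contact within 24 hours. Both points lower the stakes; neither puts attempts on the Board's immediate list.

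**Conclusion.** The point holds as a cheap improvement to safety oversight. An attempt judged unrelated has no assured prompt route to the Board: it depends on the tally being unbalanced, or on discretion under item (b). As a between-arm signal the 25% clause is close to uninformative on the relative reading, tripping by chance in 50% to 100% of cases at totals of 1 to 10.

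Those percentages rest on assumed totals, equal true rates, 30 per arm and a zero-count arm taken as a trip. The zero-count convention matters mainly at the smallest totals. The percentage-point reading removes the chance trips, but would leave the clause silent through a total of 7. The wait for missed events is up to 12 months on the literal wording and about 6 on the kinder one, and the two statements on data flow need reconciling in either case.

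The documents do not support saying that attempts would usually be judged unrelated, or that most participants would have finished treatment before the Board heard. They give neither a relatedness expectation nor an accrual timeline.

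**What to change.** - Add every suicide attempt and every death, whatever the relatedness or arm, to the events reportable to the DSMB as soon as they are recognized.
- Do not rely on the 25% clause as the trigger for unrelated SAEs. If it is kept, state whether 25% is relative or in percentage points, which events are counted, how a zero-count arm is handled and when the tally is checked.
- Send the by-condition data package before each of the two yearly meetings. Have the study coordinator, who already conducts the randomization, or other non-investigator staff prepare it and send it direct to the Board.

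The cost is protocol and DSMB-procedure wording, a few more notices in a trial of up to 60 people, and one more data package a year. Clinical management of participants does not change.
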